### **9.2 SAMPLE SIZE DETERMINATION**

Data will be tested for normality using the Shapiro-Wilk test. Continuous variables will be described as mean  $\pm$  standard deviation (SD) if normally distributed. Variables with skewed distribution (i.e. aldosterone, BNP, etc.) were logarithmically transformed prior to analyses and are presented as median and interquartile range (IQR). Categorical variables will be expressed as numbers (percentages).

When data are normally distributed, comparisons between the treatment (sodium intake) and control (placebo) groups will be made using paired Student's t-tests, and when data are non-

[figure not shown]
normally distributed, the Mann-Whitney U test will be employed. Chi-square test will be used for categorical variables. Tests for sodium intake effect on the primary outcomes without correction for period effect will be done using Mann-Whitney test on the differences. Tests for period effect will be assessed using two-sample Wilcoxon tests on the differences between treatment groups, and tests for carry-over effect will be assessed by a two-sample Mann-Whitney test on the averages in the two treatment periods. Correlations were determined with Pearson's correlation coefficient.

Additionally, we will evaluate the effects of sodium intake on changes in blood pressure, 24-hr ambulatory blood pressure monitoring (ABPM), biochemical markers, vascular functions, and specific transcriptome and epigenome by using a linear mixed model, with subject as a random effect, thereby accounting for the period, sequence, and carryover effects and to model the various sources of intra-individual and inter-individual variability. All statistical tests will be two-sided and P values  $<0.05$  will be regarded as significant. Statistical analyses will be carried out using SAS software (SAS Institute, Inc., Cary, NC, USA).

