**Sample size and statistical power:** We expect to enroll and randomize a total of 40 eligible subjects for this protocol. The sample size is assessed to detect meaningful effects of sodium intake on the study's primary outcomes and secondary outcomes, including changes in vascular function (PWV m/s), sitting SBP and DBP (mm Hg), ABPM (mm Hg), biochemical markers (plasma aldosterone, pg/mL, brain natriuretic peptide (pg/mL), as well as epigenome, transcriptome, and microbiome under an assumption about the effect size, standard deviation outcomes, correlation of measurements within individual. We estimated that a sample size of 28 participants will be required in a cross-over study to detect changes in PWV between high salt intake and control groups of 0.6 m/s (estimates based on [Pimenta et al.](#) ), with 80% power and  $P < 0.05$ , assuming common SD of 0.9 m/s for high sodium intake and control groups, and correlation of 0.3 within subjects (Figure 2). Accounting for a potential of 20% dropout during the study, the sample size would be 34.

In addition, the estimated sample size will provide us with more than 80 percent power to detect a difference of 6 mm Hg (SD=9 mm Hg) in sitting SBP between sodium intake and the placebo treatment at 0.05 significance level (estimates based on [Tzemos et al.](#) ). Similarly, the proposed sample size would give more than 90% power to detect significant changes in plasma aldosterone (pg/ml) and brain natriuretic peptide (pg/mL) between high sodium intake and control at 0.05 significance level . The sample size calculation was performed using a paired *t* test assuming no carryover effect and no interactions between subjects, treatments, and periods.

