#### 9.4.2 Analysis of the Primary Endpoints

The two primary endpoints are vascular function and microbiome.

First, vascular function difference between placebo and treatment (salt intake) will be estimated. Then, microbiome differential between treatment and placebo will be identified and estimate for each of the microbiome collection sides (skin, oral and gut). Details of the vascular function and microbiome analyses with respect to treatment and placebo are provided below.

Vascular function (e.g. pulse wave velocity, PWV) will be first analyzed as a continuous variable. Its relationship with salt intake will be investigated through multiple linear regression with vascular function as outcome and salt intake (a binary variable with two categories:

treatment and placebo) as exposure variable. For this analysis only samples with complete data for vascular function and salt intake will be considered. The outcome variable will be log transformed if it departs markedly from the Gaussian distribution. The aim of this first analysis is to estimate the effect of salt intake on vascular function. The effect size, p-value and 95% confidence interval will be provided as results.

The second endpoint is microbiome; the microbiome data of each of the all the collection sites (oral, gut and skins) will be analyzed separately. Prior to investigating the relationship between microbiome and salt intake, the raw microbiome data requires extensive processing and quality controls (QC) because of challenges posed by this type of data and the potential of spurious results if appropriate QC are not applied. The raw data will be processed in mainly 5 steps: (a) reads preparation (assembly of paired reads, filtering of low quality reads and identification of unique sequences), (b) Operational Taxonomic Units - OTU clustering (selection of unique OTU sequences), (c) quality controls (identification and removal of artifacts from amplicon reads, in OUT sequences). These tasks will be carried out using pipelines included in the standards operating protocols (SOPs) developed and used by the NIH Human Microbiome Project. For the metagenomic microbiome data, the *HUMANN2* pipeline will be used and for the 16s microbiome data the *DADA2* pipeline will be used.

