The output of the pipelines are count data which are discrete, not continuous, and include only positive values. The counts,  $C_{ij}$ , are the observed number of microbes for the  $i^{th}$  sample and  $j^{th}$  feature where the features are the OTUs or microbial taxa. The data are normalized because library sizes (total counts for each sample, across all features) often have a large magnitude difference, which can cause a bias. The data are right skewed with, usually, a large number of data points having the value 0. Such data follows a Poisson distribution and therefore a Poisson regression model type (e.g. negative binomial model) will be used to investigate the relationship between microbiome and salt intake. For each feature, a model will be fitted with the feature as outcome and salt intake (a binary variable with two categories: treatment and placebo) as covariate. The differential count (fold change difference) between treatment and placebo will be estimated for each feature (OTU). To adjust for the multiple testing of several OTUs, a false discovery rate penalty will be applied and only fold changes with an adjusted p-value (Benjamini-Hochberg multiple test correction) smaller or equal to 0.05 will be considered statistically significant.

The analysis describes above using a Poisson regression model assumes the features (OTUs) are independent but it has been shown that microbial communities do interact in such way that changes in one feature affect another feature. However, the number of interactions can be large due to the number of features, and not easily fitted in a conventional regression model. Therefore, a machine learning algorithm (Random Forest or Neural Network) will be used to investigate the combined response of the features to salt intake. These algorithms can incorporate multiple and complex interactions between features without making an assumption about their distribution. The features will be used as predictor variables to predict salt intake (a binary variable with two categories: treatment and placebo). The results will be presented as the area under the curve (AUC) of a receiver operating curve (ROC) that reflect how well the features can predict treatment and placebo. Because these ensemble techniques do not assume the predictors

variable (OTUs) are independent, no multiple testing penalty is required but rather cross-validation will be undertaken.

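### The microbiome classifier AUC, presented at three body sites under a primary endpoint, has no interval or null test, and its algorithm is not fixed

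*Combined protocol and SAP*

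**What the plan says.** Section 9.4.2 makes the microbiome one of two primary endpoints and states that "the microbiome data of each of the all the collection sites (oral, gut and skins) will be analyzed separately". It gives the microbiome two analyses. The first is a count regression for each OTU, with a fold change called significant only if its Benjamini-Hochberg adjusted P-value is at most 0.05. The second allows for interacting OTUs: "a machine learning algorithm (Random Forest or Neural Network) will be used to investigate the combined response of the features to salt intake". The OTUs predict treatment versus placebo, and the result is presented as the area under an ROC curve. The section then says that these techniques do not assume independent predictors, and so "no multiple testing penalty is required but rather cross-validation will be undertaken".

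For the AUC it gives no interval, test, reading threshold or fold scheme, and no rule for choosing between the two algorithms. Nothing elsewhere fills this in. Section 9 says there will be no formal SAP. Section 9.2 sets a general level of 0.05 ("All statistical tests will be two-sided") but names no test for an AUC. Section 9.4.9 rules out exploratory analyses, so the classifier cannot be read under that label.

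**The concern.** Elsewhere the plan gives the reader something to judge a result by: an effect size, P-value and 95% confidence interval for vascular function and blood pressure, FDR control for gene expression, and a genome-wide threshold with P-value and interval for methylation. The classifier sits under a primary endpoint and has none of these.

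Cross-validation answers a different question. It removes the optimism of scoring a model on its own training data. It does not say how widely an honest AUC scatters around 0.5 when salt does nothing and there are 28 to 40 participants. Without that reference, a reader shown 0.61 at one of three sites cannot tell a weak signal from noise. The open choice of algorithm adds a decision that could be made after the data are seen.

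**Working it through.** **The plan's own figure.** The only sample size computed is for PWV: "We estimated that a sample size of 28 participants will be required in a cross-over study to detect changes in PWV", for a difference between "high salt intake and control groups of 0.6 m/s", "with 80% power and" 5% significance, "assuming common SD of 0.9 m/s for high sodium intake and control groups, and correlation of 0.3 within subjects".
- SD of the paired difference = 0.9 × √(2 × (1 − 0.3)) = 1.065 m/s; standardised effect = 0.6/1.065 = 0.563.
- A paired t test reaches power 0.805 at 27 participants and 0.820 at 28, so the stated 28 is reproduced.
- This says nothing about the AUC. The plan gives no power, threshold or chance range for the classifier.

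**Inputs for the AUC.** Planned enrolment is 40 (section 9.2); the addendum in section 12 reports 28. There are three sites. I assume complete data, one sample per participant per treatment at each site, and one algorithm.

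**Null spread of one AUC.** With n samples per condition treated as independent, the Mann-Whitney variance gives SD = √((2n + 1)/(12n²)).
- n = 28: √(57/(12 × 28 × 28)) = 0.078; one-sided 5% point 0.628.
- n = 40: √(81/(12 × 40 × 40)) = 0.065; one-sided 5% point 0.607.

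**Chance of a given AUC with no salt effect.** One site: p = upper normal tail of (AUC − 0.5)/SD. At least one of three independent sites: 1 − (1 − p)³.

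| AUC at or above | n=28, one site | n=28, any of three | n=40, one site | n=40, any of three |
|---|---|---|---|---|
| 0.60 | 9.9% | 27% | 6.2% | 17% |
| 0.62 | 6.2% | 17% | 3.2% | 9% |
| 0.65 | 2.7% | 7.9% | 1.05% | 3.1% |
| 0.70 | 0.5% | 1.5% | 0.1% | 0.3% |

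**Check by simulation (n = 28, no salt effect, 5-fold cross-validation, both samples of a person in the same fold).**
- 334 replicates, 100 count features: SD 0.077 (Random Forest) and 0.076 (network). P(AUC ≥ 0.62) = 0.057 for either, so over three sites 1 − 0.943³ = 16%, against 17% by formula.
- A separate run of 89 replicates, 150 features: SD 0.070 and 0.066. P(AUC ≥ 0.60) was 11.2% for Random Forest (30% over three sites) and 4.5% for the network (1 − 0.955³ = 13%). With 89 runs these are rough.
- Two linear classifiers, which the plan does not name, gave SD 0.065.

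Feature counts and variance components in the simulations are assumed. Across them the null SD at 28 participants lies between 0.065 and 0.077, so the formula's 0.078 is at the upper end.

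**Sites are not truly independent.** They share participants and treatment labels. If their AUCs moved together completely, the any-site figure would fall to the one-site figure. For AUC ≥ 0.60 the range is therefore 9.9% to 27% at 28 participants and 6.2% to 17% at 40.

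**The case against.** The strongest defence is that the plan never treats the AUC as a test. Benjamini-Hochberg at 0.05 is the only significance rule for the microbiome; the classifier comes after it, and its AUC is merely presented. That stands. A reader might infer that the two analyses compete to decide the endpoint and that the sponsor could conclude either way. The text does not support this: the order of precedence is implicit, but it can be read.

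A reader might also infer that the multiplicity sentence is simply wrong. In context it contrasts with the per-OTU penalty in the paragraph before. One classifier yields one global AUC, so no per-OTU penalty is needed. The conclusion is right for OTUs, although the reason given (predictors need not be independent) is poor. The sentence makes no claim about sites or algorithms, and those remain uncovered.

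A third tempting reading is that both algorithms will be fitted and the larger AUC reported. At 28 participants over three independent sites, the 334-replicate simulation then puts the chance of AUC ≥ 0.62 at 1 − (1 − 0.102)³ = 28% (Monte Carlo range about 19% to 35%) and of AUC ≥ 0.60 at about 39%. The plan says one or the other and describes no such selection, so these are worst cases.

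Finally, fold formation may matter more than sampling noise. Section 8.2.2 lists four skin swabs per visit. In small simulations (about 30 runs per setting), splitting swabs across folds gave a mean null AUC of 0.52, 0.62 or 0.82 for an assumed visit-level variance share of 0.1, 0.2 or 0.4; participant-level folds kept it at 0.49 to 0.51. The plan does not say that it will split swabs, so this is a reason to fix the fold unit and not a demonstrated error.

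**Conclusion.** The concern holds in modest form. The AUC at each of three sites has no interval or null reference, and the algorithm is open. As planned, an AUC of 0.60 to 0.62 cannot be told from chance. With one algorithm, at least one site reaches 0.60 by chance in up to about 27% of trials with 28 participants, or 17% with 40; for 0.62 the figures are about 16% (simulated) and 9%. An AUC of 0.70 or more is unlikely to be noise if folds are formed by participant: 1.5% or less.

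These sizes rest on reading points that the plan does not set, on samples treated as independent, and on independent sites. The documents do not support a claim that the plan would declare a false microbiome effect significant. This is a cheap improvement to make before unblinding, not a flaw that undermines the endpoint.

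**What to change.** In section 9.4.2:
1. Name one algorithm and its tuning before unblinding.
2. Keep all samples of a participant, including all skin swabs and both periods, in one fold.
3. Report each site's AUC with a permutation P-value: swap the salt and placebo labels within participant, refit the full cross-validation each time, and Holm-adjust over the three sites. Within-participant swaps match the cross-over randomisation.
4. State that the classifier is supportive of the Benjamini-Hochberg controlled feature analysis.
5. Reword, without deleting, the multiplicity sentence: no per-OTU penalty is needed because each classifier gives one global AUC, while the site-level tests are adjusted.

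The cost is protocol wording and some computing time; no new data are needed. The downside is that a modest AUC can no longer stand as evidence by itself.

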#### 9.4.3 Analysis of the Secondary Endpoint(s)

The secondary endpoints will be assessed independent of the results associated with the primary endpoints; secondary endpoints include blood pressure, whole blood epigenome, and whole blood and urine transcriptome. The effect of treatment and placebo will be investigated will be investigated for each secondary endpoint, as detailed below.

The association between blood pressure (systolic and diastolic) and salt intake will be assessed using multiple linear regression with salt intake (two categories: treatment and placebo) as the exposure variable and blood pressure outcome variable. The effect size, p-value and 95% confidence interval of the regression model will be provided as results.

The effect of salt intake on gene expression will be investigated in a differential expression analysis to identify genes whose expression differs significantly between treatment and placebo. The gene expression data will be normalized, using the weighted trimmed mean of M-values (TMM) method, an optimal method for the normalization of mRNA count data. Genes with an expression less than 1 Count Per Million (CPM = count/sum [counts] x 1million) in at least 2 samples will be excluded because results from genes with extremely low expression are not reliable. Gene expression is generated as count data which follows a Poisson distribution; therefore, a negative binomial model will be fitted using the R library *edgeR* developed to handle the specificities of mRNA sequencing data. The model computes likelihood ratio tests for the coefficients whilst taking into account dispersion. A deviance of goodness of fit test will be carried out to identify genes where the model fit was poor indicating that the dispersion estimate is away from the average dispersion. Dispersion outliers will not be considered for the results because the deviance indicates low quality or marked expression difference for the gene. Finally, genes with a log fold change not equal to 0 and a false discovery rate adjusted p-value  $\leq 0.05$  will be reported as significantly differentially expressed between treatment and placebo. Multiple testing correction, for the total number of genes considered, will be carried out using the Benjamini-Hochberg method.

The epigenetic effect of salt intake will be investigated through a two-sample t-test to identify methylation sites with significant methylation level difference between treatment and placebo. At a minimum of 5X coverage and an average coverage of 30X, the SureSelect-MethSeq (SS-Methseq) platform captures between 2.6 and 2.3 million methylation sites. After thorough processing and QC of the methylation data, using the Bismark pipeline, samples and methylation sites that passed all QC filters will be considered for the analysis. Each methylation site will be treated as a continuous variable and salt intake will be treated as a nominal variable with two categories (treatment and placebo), in the t-test. In such analysis, the methylation sites are assumed to be independent and there is, hence, a high burden of multiple testing due to the millions of sites being tested. Therefore, a significance threshold of p-value  $< 9 \times 10^{-8}$  will be applied to control for false positive findings; this threshold was derived from empirical work based on the Illumina EPIC array which has a lower density than the SS-Methseq platform but includes carefully selected sites that span the whole genome. The estimated mean difference, p-value and 95% confidence interval of the t-test will be presented as the results.

After the transcriptome, epigenome and microbiome data have been considered separately in the analyses described above and to understand the links between gene expression and methylation, an ensemble technique such as Random Forests will be used to leverage the high dimensionality of the data (number of features >> number of observations) and identify the best combination of predictors of salt intake in the transcriptome and epigenome data. Subsequently, the OTUs identified in the microbiome data will be integrated to find out if microbiome information improves the prediction accuracy of the omics data. This will provide further insights into the interplay between the three domains (microbiome, transcriptome and epigenome).

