## **9 STATISTICAL CONSIDERATIONS**

The protocol will not have a formal Statistical Analytical Plan (SAP).

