**Figure 2.**

### 9.3 POPULATIONS FOR ANALYSES

We will use the per-protocol analysis dataset for our study. We are confident that participants will comply with the protocol sufficiently to ensure that the data will be likely to represent the effects of exposure to treatment and placebo arms based on the underlying scientific model.

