## 12 ADDENDUM FOR TRANSFER OF GENEFORECAST DATA

GENE-FORECAST (GENomics, Environmental FactORs and the Social DEterminants of Cardiovascular Disease in African Americans Study) was established to explore the intricate relationship between the unique genomic variations characteristic of African-Americans (AA) and the broader array of social determinants and environmental factors, collectively known as the 'exposome', that impact the development of cardiovascular disease (CVD) in this population.

The Sodium Intervention Trial (SIT) is a clinical trial protocol (000070) aimed at investigating the impact of dietary salt on the cardiovascular system, leveraging the existing pool of participants of the GENE-FORECAST protocol (18-HG-0048). Initially embedded within GENE-FORECAST, SIT sought to enroll participants who had previously consented to be re-contacted. However, as guidelines prohibited the inclusion of a sub-study within an ongoing natural history protocol, SIT was separated from GENE-FORECAST after recruiting an initial cohort of 20 participants.

Following the division of the protocols, an additional 8 participants were enrolled in SIT, resulting in a total of 28 participants. To conduct comprehensive analyses of the SIT clinical trial data, it is imperative to have access to the baseline characteristics of all 28 participants recruited from the

GENE-FORECAST protocol. Therefore, we kindly request the transfer of data pertaining to these 28 participants from the GENE-FORECAST protocol to the SIT protocol.

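### As written, the RNA-seq filter drops any gene below 1 CPM in two or more samples, however well it is expressed in the rest

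*Combined protocol and SAP*

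**What the plan says.** Section 9.4.3 of the combined protocol and SAP describes the gene expression analysis for the secondary transcriptome endpoint. Its aim is "to identify genes whose expression differs significantly between treatment and placebo". After normalisation and before the negative binomial model is fitted, it applies a low-expression filter: "Genes with an expression less than 1 Count Per Million (CPM = count/sum [counts] x 1million) in at least 2 samples will be excluded". The reason follows in the same sentence: "because results from genes with extremely low expression are not reliable". The genes that remain are tested, and the false discovery rate is controlled over that set: "Multiple testing correction, for the total number of genes considered, will be carried out using the Benjamini-Hochberg method".

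The count of two refers to samples in general. It is not tied to a treatment condition or to a share of the samples. No other section restates the filter, and section 9 opens by stating that there will be no formal SAP. This sentence is therefore the only specification of the filter in the documents.

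**The concern.** A low-expression filter is meant to remove genes with too few reads almost everywhere to be informative. This sentence instead removes a gene as soon as two samples fall below the cut-off, even if all the others are well above it. That conflicts with the reason given, since a gene that passes in nearly every sample does not have extremely low expression. It also works against the aim, since a gene low under one treatment and expressed under the other is a difference the analysis is looking for.

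The wording can be coded exactly as it stands and will run without error. The literal rule and the probably intended one give different sets of tested genes. Because the Benjamini-Hochberg correction runs over the genes considered, they also give different adjusted p-values. With the direction left uncertain, the choice could be made after the data have been seen.

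**Working it through.** The plan states no figure for the filter's effect, so there is none to reproduce. The check is a count, followed by an illustration.

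**Inputs from the documents**
- Cut-off 1 CPM; trigger 2 samples (section 9.4.3).
- Planned size, section 9.2: "We expect to enroll and randomize a total of 40 eligible subjects for this protocol".
- Number enrolled, section 12 addendum: "resulting in a total of 28 participants".
- Blood and urine are scheduled at all four visits (section 1.3, Table 2). Section 9.4.3 does not say which visits' samples enter the filter.

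**Assumption on sample numbers.** One end-of-period sample per participant per condition: 28 × 2 = 56 samples, or 40 × 2 = 80. The analysis set is per-protocol (section 9.3), so the actual numbers may be smaller.

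**Step 1: counting, with no assumption on depth or dispersion**
- The trigger as a share of all samples is 2/56 = 3.6% or 2/80 = 2.5%.
- A gene at or above 1 CPM in 54 of 56 samples (96%) or 78 of 80 (97.5%) is excluded.
- A gene below 1 CPM in every sample of one treatment has 28 or 40 low samples against a trigger of 2, so it is always excluded, whatever its level under the other treatment.

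**Step 2: genes that are low only sporadically.** Let q be the chance that one sample of a given gene falls below 1 CPM, with samples independent. Both are assumptions; the documents give neither read depth nor dispersion. Under the literal rule

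P(excluded) = 1 − [(1 − q)^n + n·q·(1 − q)^(n−1)]

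| q (assumed) | n = 56 | n = 80 |
|---|---|---|
| 1% | 0.108 | 0.191 |
| 2% | 0.309 | 0.477 |
| 5% | 0.777 | 0.914 |
| 10% | 0.980 | 0.998 |

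For q = 1% and n = 56: 0.99^56 = 0.570 and 56 × 0.01 × 0.99^55 = 0.322, so P = 1 − 0.892 = 0.108. If all four visits counted, n would be 112 or 160, and q = 1% would give 0.309 or 0.476. The trigger stays at 2 while n grows, so the rule becomes stricter as the trial gets larger.

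**Step 3: which expression levels are exposed.** For scale only, assume 20 million reads per sample and negative binomial counts with dispersion 0.16.

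| Mean CPM | P(one sample < 1 CPM) | Excluded, n = 56 | Excluded, n = 80 |
|---|---|---|---|
| 2 | 0.093 | 0.972 | 0.996 |
| 3 | 0.020 | 0.307 | 0.475 |
| 5 | 0.0019 | 0.005 | 0.010 |
| 10 | 0.00005 | < 0.0001 | < 0.0001 |

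Under these assumptions the loss falls on genes within a few CPM of the cut-off and has nearly vanished by 5 CPM.

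**Step 4: the same count with the direction reversed.** If a gene is kept when at least 2 samples reach 1 CPM, a gene at 0.5 CPM throughout one treatment and 20 CPM throughout the other has 28 or 40 passing samples and is kept.

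**The case against.** The best defence is that this is a slip of wording. The sentence gives its own purpose, removing genes with extremely low expression, and an experienced analyst would probably code the conventional keep rule. That is likely correct, and it makes this a clarification and not a design flaw. It does not make the clarification unnecessary: nothing else in the documents states the intended direction, and no SAP is planned that would.

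Three other limits stand. First, the filter ignores treatment, so what has been shown is lost genes; neither false positives nor bias in the genes that remain has been demonstrated. Second, the practical loss depends on read depth and dispersion, which are not given, so the percentages above are illustrations. Third, the same paragraph later discards dispersion outliers, partly because they may show a marked expression difference. Some strongly responding genes could be lost at that step even with the filter corrected.

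A reader might infer that the trial will lose its strongest sodium responders. The documents do not support that. They do not predict that any gene is silenced under one condition. A gene that is merely lower under one treatment, but comfortably above 1 CPM there, is not caught by the counting argument.

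**Conclusion.** The rule is wrong as written and should be corrected before the expression analysis is run. Taken literally, it excludes genes that pass in 96% to 97.5% of samples and every gene below 1 CPM throughout one treatment, contrary to both the reason and the aim stated beside it. The counts rest only on one end-of-period sample per condition and 28 or 40 participants. The exclusion probabilities of 11% and 19% (q = 1%) or 31% and 48% (q = 2%) rest in addition on an assumed per-sample rate and independent samples.

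The consequence is limited to one secondary endpoint, the blood and urine transcriptome. The primary endpoints are untouched, and genes well expressed in both conditions are mostly unaffected.

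**What to change.** Replace the sentence with a keep rule, applied without reference to treatment and separately to blood and urine: keep a gene if it reaches 1 CPM or more in at least a pre-stated number of analysed samples, and exclude it otherwise. State which visits' samples count.

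- **Minimum correction:** set the number at 2. This cures the direction error. It is permissive: a gene with an assumed 5% chance per sample of reaching 1 CPM would be kept with probability 0.78 (56 samples) or 0.91 (80).
- **Optional stricter version:** set the number below the per-condition sample count, for example about 70% of it (0.7 × 28 = 19.6, so 20; 0.7 × 40 = 28). The 70% is only an example; nothing in the documents fixes it. Base it on the samples actually analysed, because section 9.3 says "We will use the per-protocol analysis dataset for our study".

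The change is one sentence and needs no new data. Its cost is that more genes are tested than under the literal rule, so the Benjamini-Hochberg burden rises. The documents give no gene counts from which to compute by how much.
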